This is a non-interventional prospective, single center, bilateral, non-randomized, open-label, observational clinical study. All patients will have had bilateral implantation of an Eyhance IOL at the time of cataract surgery. These patients will then be assessed in the 1–6-month post-operative period. Patients will be grouped into two arms: “distance with minimal intermediate” and “distance with enhanced intermediate/near” based on mean photopic binocular BCDVA and DCIVA (at 66 cm) of patients with bilateral Eyhance IOLs corrected to plano sphere. The “distance with minimal intermediate” group is defined by BCDVA of 0.1 logMAR or better but a DCIVA of 0.4 logMAR or worse. The “distance with enhanced intermediate/near” is defined by BCDVA of 0.1 logMAR or better and a DCIVA of 0.3 logMAR or better. In addition to binocular BCDVA and DCIVA, monocular measurements will be obtained as well. The two groups will be compared to assess which patient biometric properties (such as spherical aberration, q value, pupil size, etc) lead to an overall increase in near or intermediate vision as well as overall patient satisfaction. Biometric data will be obtained from the Zeiss IOL Master 700, Atlas 9000, and the iDesign.

Duration:

3 months or longer to meet required enrollment.

Administration:

Patients with previously implanted bilateral Eyhance IOLs will be offered the opportunity to participate in the study.

Visit Schedule:

All subjects will undergo 1 visit. At the study visit and after informed consent, the subjects' demographic information will be collected, and the subject will have the following testing:

- 1) Manifest refraction
- 2) Best corrected distance visual acuity
- 3) Distance corrected intermediate visual acuity
- 4) Distance corrected near visually acuity
- 5) Binocular best corrected distance visual acuity
- 6) Binocular distance corrected intermediate visual acuity
- 7) Binocular distance corrected near visually acuity
- 8) Pupil measurements (photopic and/or mesopic – automated and manual)
- 9) Review or remeasurement of biometry (IOL Master 700 or Atlas 9000 topography)
- 10) iDesign measurement

STUDY POPULATION CHARACTERISTICS:

Condition

Patients with healthy eyes and bilateral implantation of Eyhance IOLs.

Number of Subjects:

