Per Green, for multiple variables in a regression analysis, $N = 50 + 8(m)$ per arm should be sufficient for appropriate power, assuming a beta of 0.2 and an alpha of 0.05 for a power of 80%. Assuming 6 variables (pupil size, q value, spherical aberration, AC depth, axial length, average K power), approximately 110 patients (220 eyes) will be required.

Source: Green, Samuel B. "How Many Subjects Does It Take To Do A Regression Analysis." *Multivariate behavioral research* 26 3 (1991): 499-510 .

Inclusion/Exclusion Criteria (all study criteria apply to each study eye unless otherwise indicated):

Inclusions

- 1) Adults, 40 years of age having already undergone uncomplicated cataract removal by phacoemulsification with a clear corneal incision in both eyes.
- 2) Implantation of bilateral Eyhance IOLs (DIB00/DIU***).

- 3) Able to comprehend and willing to sign informed consent and complete all required testing procedures
- 4) Best Corrected Distance Visual Acuity (BCDVA) projected to be 0.10 logMAR (Minimum Angle of Resolution) or better
- 5) Clear intraocular media
- 6) Minimum of two weeks post YAG capsulotomy to treat PCO

Exclusions

Subjects will not be permitted to enroll in this study if they meet any of the following exclusion criteria:

- 1) Any corneal abnormality, other than regular corneal astigmatism (as determined by pre-operative testing) that in the opinion of the investigator would confound the outcome(s) of the study
- 2) Any complication during cataract surgery (capsular tear, vitrectomy, etc)
- 3) History of or current retinal conditions or predisposition to retinal conditions
- 4) Amblyopia or strabismus in either eye
- 5) History of or current anterior or posterior segment inflammation of any etiology
- 6) Any form of neovascularization on or within the eye
- 7) Glaucoma (uncontrolled or controlled with medication)
- 8) Optic nerve atrophy
- 9) Subjects with diagnosed degenerative eye disorders
- 10) Postoperative CDVA worse than 0.10 logMAR (20/25 snellen).
- 11) Subjects who have an acute or chronic disease or illness that would confound the results of this investigation in the opinion of the investigator (e.g. immunocompromised, connective tissue disease, clinically significant atopic disease, etc)

EVALUATION CRITERIA:

The main objective of this study is to demonstrate which biometric characteristics can lead to enhanced intermediate or near vision in patients with prior bilateral Eyhance implantation.

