Primary Clinical Endpoints:

- 1) To compare two groups categorized by “distance with minimal intermediate” and “distance with enhanced intermediate/near” based on mean photopic binocular BCDVA and DCIVA (66 cm) of patients with bilateral Eyhance IOLs targeted corrected at plano sphere.
- 2) To determine if any statistically significant differences in biometric data exists between the two groups including pupil size, spherical aberration, q value, etc. that may allow for pre-operative recognition of those patients who could have enhanced benefits of the Eyhance IOL. This will require multiple regression analysis given the large number of variables.
- 3) Comparison of a patient satisfaction survey between the two groups to assess for subjective differences in everyday life to determine if the enhanced vision plays a statistically significant difference in patients’ perceived quality of vision or quality of life.

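### Endpoint 2 sets eye-level biometry against one binocular result per patient: the unit of analysis is not stated, monocular intermediate acuity goes unused, and 220 eyes carry at most 110 independent outcomes

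*Combined protocol and SAP*

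**What the plan says.** All references are to the combined protocol and SAP.

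- **Grouping (Overall Study Design).** "Patients will be grouped into two arms", "based on mean photopic binocular BCDVA and DCIVA (at 66 cm) of patients with bilateral Eyhance IOLs corrected to plano sphere". The enhanced group "is defined by BCDVA of 0.1 logMAR or better and a DCIVA of 0.3 logMAR or better"; the minimal group "is defined by BCDVA of 0.1 logMAR or better but a DCIVA of 0.4 logMAR or worse". Primary Clinical Endpoints, item 1, repeats the binocular basis. Each patient therefore has at most one label.
- **Predictors.** "Biometric data will be obtained from the Zeiss IOL Master 700, Atlas 9000, and the iDesign". Number of Subjects names six variables: pupil size, q value, spherical aberration, anterior chamber depth, axial length and average K. All are properties of a single eye.
- **Monocular acuity.** "In addition to binocular BCDVA and DCIVA, monocular measurements will be obtained as well". The Visit Schedule lists distance-corrected intermediate acuity (DCIVA) separately from its binocular counterpart. No grouping rule, endpoint or model refers to the monocular value.
- **Size (Number of Subjects).** The rule is N = 50 + 8m per arm with m = 6, and the conclusion is that "approximately 110 patients (220 eyes) will be required".
- **Analysis (Primary Clinical Endpoints, item 2).** Multiple regression is named. The text does not say whether a record is an eye or a patient, how two eyes' biometry maps to one binocular label, or how correlation between fellow eyes is handled.

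**The concern.** The study exists to find which biometric features go with better intermediate or near vision. Its predictors vary by eye, but the outcome used to study them does not. Two things follow.

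First, the eye count invites an analysis with 220 rows in which each binocular result appears twice. Fellow eyes have similar biometry, so such rows are not independent and standard errors that ignore this are too small. The stake is false-positive predictors in a primary endpoint meant to guide pre-operative recognition of patients.

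Second, when a patient's eyes differ in intermediate vision, the binocular label cannot show which eye's biometry went with the better result. As an illustration, eyes at 0.25 and 0.42 logMAR might well give a binocular DCIVA of 0.3 or better. The monocular measurement that would separate them is taken at the same visit and then not used.

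**Working it through.** **1. The plan's own size.** With m = 6, 50 + 8 × 6 = 98, not 110. Read as a total, 98 is exceeded by 110 patients. Read per arm, as written, it is 2 × 98 = 196, which 110 patients do not reach; only 220 eyes exceed it. No dropout allowance is stated. (That 98 does not reproduce 110 is a separate issue. Here it matters only because the eye count is what meets the per-arm rule.)

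**2. Independent outcomes.** One binocular label per patient × 110 patients = at most 110. Patients with binocular DCIVA between 0.3 and 0.4 fall in neither group, so the grouped analysis may have fewer.

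**3. Error rate if 220 eyes were treated as independent.** Two eyes share the outcome exactly, and their biometry has correlation r (assumed; the documents give none). Variance inflation is 1 + r, effective N is 220/(1 + r), and the actual two-sided error is 2 × [1 − Φ(1.96/√(1 + r))]. For r = 0.8: 220/1.8 = 122; 1.96/√1.8 = 1.46; error 14.4%. The last two columns come from 1,500 simulated studies per row, each with 110 patients, an even chance of either group and six predictors with no true effect.

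| r | Effective N | Error, formula | Error, 220 eyes (simulated) | Error, patient means (simulated) |
|---|---|---|---|---|
| 0.5 | 147 | 11.0% | 11.4% | 5.4% |
| 0.8 | 122 | 14.4% | 14.8% | 4.9% |
| 0.9 | 116 | 15.5% | 16.5% | 5.1% |
| 0.95 | 113 | 16.0% | 16.7% | 5.3% |

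Patient-clustered standard errors on the 220 rows also give about 5%.

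**4. Eyes whose own result disagrees with the label.** The documents give no mean, SD or fellow-eye correlation for DCIVA and no binocular gain, so only a range under assumptions is possible. Binocular acuity is taken as the better eye's acuity plus a fixed gain. The share of eyes in enhanced patients that are themselves 0.4 or worse is:

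| Mean DCIVA | SD | Fellow-eye correlation | Gain | Share 0.4 or worse |
|---|---|---|---|---|
| 0.30–0.35 | 0.10 | 0.5–0.9 | 0–0.05 | 0.1–12% |
| 0.35–0.42 | 0.12 | 0.5–0.7 | 0.04 | 8–20% |
| 0.35–0.42 | 0.12 | 0.9 | 0.04 | 2–4% |
| 0.25–0.30 | 0.12 | 0.7–0.9 | 0.04 | about 1–6% |

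The overall span is from under 1% to about 20%, and the share falls as fellow eyes become more alike.

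**5. What the unused measurement could add.** Assuming a correlation of 0.25 between an eye's biometry and its own DCIVA, simulated power was 83–93% for monocular DCIVA with patient clustering, 67–81% for continuous binocular DCIVA with one record per patient, and 42–65% for the two binocular groups with one record per patient. Error rates stayed at 4.5–7%. Part of the gain over the groups comes from keeping the outcome continuous and retaining patients between 0.3 and 0.4; the middle figure separates that part out.

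**The case against.** The strongest reply is that nothing in the protocol commits to analysing eyes. Patients are grouped, the comparison is of patients' biometric properties, and the aim is to recognise patients who may benefit. In a study where everyone has two implants, 220 eyes in brackets may be plain arithmetic, and 110 patients satisfy the rule if 98 is a total. This stands. A reader might infer that the plan double-counts each binocular result; the documents do not support that. They leave the question open, and the per-arm wording only makes the eye-level reading plausible.

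It can also be said that binocular vision is what the patient experiences, that it matches the satisfaction endpoint, and that relating it to a patient-level summary of biometry is legitimate. This stands too: the binocular label is not in itself an error. What remains is that a patient-level analysis also needs a rule for combining two eyes, and none is given.

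Finally, fellow eyes may be so alike that little is lost. High acuity correlation does shrink the disagreement in step 4, and excluding amblyopia, strabismus and poor corrected distance acuity removes some causes of asymmetry, though not asymmetry in intermediate vision itself. But high biometry correlation raises the error in step 3, so similarity between eyes does not settle the matter.

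**Conclusion.** The point holds in a limited form. From the text alone: endpoint 2 relates six eye-level predictors to one binocular label per patient, monocular DCIVA enters no endpoint, the unit of analysis is unstated, and 220 eyes supply at most 110 independent outcomes.

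The error of about 11–17% per predictor is conditional. It applies only if eyes are analysed as independent records, and it rests on assumed biometry correlations of 0.5–0.95. A reader might also infer that a substantial, known fraction of eyes would be mislabelled. The documents do not support any particular figure, and with one record per patient no individual eye is labelled at all; the cost is then lost within-patient information. The power comparison is likewise illustrative and depends on the assumed correlation of 0.25.

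This should be changed, because endpoint 2 is listed as primary and serves the main objective. It does not invalidate the study.

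**What to change.** **Preferred.** For endpoint 2, take each eye's own monocular DCIVA as the outcome and that eye's biometry as predictors. Put both eyes in one model that allows for pairing (GEE clustered on patient, or a patient random effect). Keep the binocular groups for endpoint 3, where binocular vision is the relevant exposure.

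**If the binocular outcome is kept for endpoint 2.** Use one record per patient with a prespecified biometry summary, for example the mean of the two eyes, and state the analysis size as 110 patients rather than 220 eyes.

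Either way, state the unit of analysis in Number of Subjects and in endpoint 2.

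**Cost.** Protocol wording and a standard paired-eye model; the visit already collects the data. Under the preferred option, endpoints 2 and 3 use different levels of outcome, and the report must say so.

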Maximizing Visual Outcomes with Eyhance IOLs

NCT05611073

25 Jan 2022

PROTOCOL TITLE: Maximizing Visual Outcomes with Eyhance IOLs

STUDY TREATMENTS: None

Study Objectives:

The objective of this study is to demonstrate which pre-operative biometric findings or measurements could indicate increased intermediate or near vision in a patient receiving an Eyhance IOL.

The objective will be completed by measuring visual outcomes at distance, intermediate, and near when corrected to plano sphere as well as obtaining or reviewing biometric measurements in a controlled setting. In addition, the patients will also fill out a questionnaire to determine their level of spectacle independence and satisfaction.

Clinical Hypothesis:

Eyhance IOLs provide intermediate vision based on benchmark defocus curves. Some Eyhance patients also appear to have vastly improved intermediate and even near vision compared to other patients who have received an Eyhance IOL. This study aims to determine which biometric properties (such as spherical aberration, q value, pupil size, etc) can be targeted for these outcomes. Patients will be assessed for corrected monocular and binocular distance, intermediate, and near vision at plano. Lastly patient satisfaction score between the two groups will also be determined.

OVERALL STUDY DESIGN

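### None of the six model variables is guaranteed to be pre-operative, and AC depth from before and after lens replacement can enter the regression as one variable

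*Combined protocol and SAP*

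**What the plan says.** The Study Objectives set out to "demonstrate which pre-operative biometric findings or measurements could indicate increased intermediate or near vision". Primary endpoint 2 has the same purpose: differences between the two vision groups are sought so that patients likely to benefit might be recognised before surgery. The Evaluation Criteria restate the main objective without any reference to the time before surgery; they ask only which biometric characteristics go with better intermediate or near vision.

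On timing, Administration says "Patients with previously implanted bilateral Eyhance IOLs will be offered the opportunity to participate in the study", Overall Study Design says "These patients will then be assessed in the 1–6-month post-operative period", and the Visit Schedule says "All subjects will undergo 1 visit".

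On sources, Overall Study Design says "Biometric data will be obtained from the Zeiss IOL Master 700, Atlas 9000, and the iDesign". Item 8 of the visit is "Pupil measurements (photopic and/or mesopic", by automated and manual methods. Item 9 is "Review or remeasurement of biometry (IOL Master 700 or Atlas 9000 topography". Item 10 is an iDesign measurement. The Study Objectives leave the same choice open: "obtaining or reviewing biometric measurements in a controlled setting".

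Number of Subjects lists six variables for the regression: pupil size, q value, spherical aberration, AC depth, axial length and average K power. No section assigns each variable to a device or to a date relative to surgery.

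**The concern.** A conclusion about recognising patients before surgery needs predictors that were available before surgery. The plan is written around a single post-operative visit, and the one item that could bring in earlier records also permits a new measurement in an eye that already has the implant. A site could follow the protocol exactly and review a pre-operative record for one patient while remeasuring the next.

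For AC depth this matters most, because the natural lens has been replaced between the two measurements, so one column could hold two different quantities. At stake are a diluted or uninterpretable AC depth coefficient, and a pre-operative claim resting on post-operative data. If date and source are not recorded, the two kinds of value cannot be separated afterwards.

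**Working it through.** **Step 1. Trace the six variables to the Visit Schedule.**

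| Variable | Scheduled source | Guaranteed pre-operative? |
|---|---|---|
| Pupil size | Item 8, study visit; no earlier source named | No |
| AC depth, axial length, average K, q value | No device assigned; item 9 if from IOL Master or Atlas | No, either date allowed |
| Spherical aberration | No device assigned; item 9 (either date) or item 10 (study visit) | No |

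Count guaranteed pre-operative: 0 of 6.

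**Step 2. The plan's own sample size.** The stated rule with m = 6 gives 50 + 8 × 6 = 98 per arm, or 196 for two arms. The stated 110 is not reproduced. That is a separate matter and this point does not depend on it; 110 is used below only because it is the planned number.

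**Step 3. Illustration for AC depth.** Only N = 110, six predictors and alpha 0.05 come from the protocol. Assumed: pre-to-post shift d = 0.5, 1.0 or 1.5 mm; between-patient SD 0.4 mm (variance 0.16); share remeasured s = 10%, at random; AC depth uncorrelated with the other predictors; and f² = 0.075, chosen because it gives about 80% power at 110. The plan does not say whether its regression is linear or logistic; the power figures use a linear model.

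Slope retained = 0.16 / (0.16 + s(1 − s)d²), with s(1 − s) = 0.09:
- d = 0.5: 0.16 / (0.16 + 0.0225) = 0.88
- d = 1.0: 0.16 / (0.16 + 0.09) = 0.64
- d = 1.5: 0.16 / (0.16 + 0.2025) = 0.44

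Power comes from the noncentral F with 1 and N − 7 = 103 df and noncentrality f² × (slope retained) × N. Without mixing the noncentrality is 0.075 × 110 = 8.25 and power is 81%. With mixing, power is 76%, 62% and 47% for the three shifts. If the other five predictors explain 30% of AC depth variance, 0.16 becomes 0.16 × 0.7 = 0.112; the slope retained is then 83%, 55% and 36%, and power 74%, 56% and 40%.

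**Step 4. False positives.** In simulation with no true AC depth difference and equal mixing (10% in both groups), the test on AC depth rejects 5% of the time. With 10% mixing in one group and 20% in the other, 55 patients each, it rejects about 9% to 21% of the time over the same shifts. Adding a pre/post source indicator brings this back to about 5%.

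**Step 5. Leaving patients out compared with mixing them in.** Same assumptions, predictors uncorrelated:

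| Share without a pre-operative value | Left out | Mixed in (N = 110) |
|---|---|---|
| 10% | N = 99: 77% | 76%–47% |
| 20% | N = 88: 72% | 72%–35% |
| 30% | N = 77: 66% | about 70%–30% |

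Beyond about 20% missing, leaving patients out can cost more power than mixing if the shift is near 0.5 mm. Keeping everyone with a source indicator holds simulated power at about 77% to 78% with 10% to 30% remeasured, provided the shift is the same for all patients.

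**The case against.** The strongest reply has four parts.

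First, the protocol does not speak with one voice. The Evaluation Criteria give a main objective that post-operative biometry could satisfy, and endpoint 2 is hedged. This stands: it makes the matter partly an inconsistency between sections. It does not remove the pre-operative aim in the Study Objectives and endpoint 2.

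Second, reviewing biometry most naturally means reading the pre-operative chart, and the corneal exclusion criterion presumes that some pre-operative testing exists. This also stands in part. A reader might infer that pre-operative values will be absent, or that mixing is planned; the documents support neither. Mixing is permitted, not prescribed. But the same item allows remeasurement, and no rule governs the choice.

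Third, a reader might infer that post-operative iDesign spherical aberration necessarily includes the implant's contribution. The protocol only names the device; it does not say what iDesign measures or that spherical aberration comes from it. What can be said is that any iDesign value is scheduled at the post-operative visit.

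Fourth, the figures rest on assumed inputs and cover one variable of six. That is correct. A reader might also infer from the 9% to 21% range that spurious findings are to be expected. That range needs mixing that differs by vision group, and the documents show no mechanism for it. No figure is offered for pupil size, axial length, average K, q value or spherical aberration.

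**Conclusion.** The point holds and should be fixed. As written, the plan guarantees a pre-operative value for none of its six variables, and it allows AC depth from before and after lens replacement to be analysed as one variable. That conclusion comes from the text and needs no figure.

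The size of the effect cannot be taken from the documents. The illustrated loss, to 88%–44% of the slope and 76%–47% power, depends on the assumed shift, SD, f² and a 10% mixing share, and on mixing at random. Under those conditions the harm is loss of power and a diluted coefficient, with false positives unchanged at 5%. Confidence is medium: sites may in practice use pre-operative charts throughout, but nothing in the plan requires it.

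**What to change.** 1. Reconcile the Study Objectives and endpoint 2 with the Evaluation Criteria.
2. For the primary model, take AC depth, axial length, average K, q value and spherical aberration from dated pre-operative records. Name one device per variable and record date and source for each value.
3. Do not pool pre- and post-operative AC depth as one variable. Use remeasured values only in a sensitivity analysis that keeps all patients and includes a pre/post source indicator, stating that this assumes a constant shift.
4. Use one pupil lighting condition and one method for all patients.
5. Limit the conclusion about recognising patients before surgery to variables with pre-operative values. Report pupil size and anything measured at the study visit, including iDesign, as post-operative associations.
6. If pre-operative records prove too incomplete, adopt the Evaluation Criteria wording, association with biometric characteristics, as the objective.

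Cost: chart abstraction, a date and source field per value, and protocol wording; no extra visit. The number in the primary model may fall below 110. Under the assumptions above, losing 10% (N = 99) gives about 77% power for AC depth instead of 81%.

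### If the single open-label visit runs in its numbered order, the group is known before the manual pupil reading and the choice of biometry source, and the questionnaire has no set position.

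*Combined protocol and SAP*

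**What the plan says.** All references are to the combined protocol and SAP.

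- **Masking.** Overall Study Design describes an "open-label, observational clinical study". No masked examiner, grader or analyst is mentioned anywhere.
- **Grouping.** The same section groups patients "based on mean photopic binocular BCDVA and DCIVA (at 66 cm) of patients with bilateral Eyhance IOLs corrected to plano sphere". The minimal-intermediate "group is defined by BCDVA of 0.1 logMAR or better but a DCIVA of 0.4 logMAR or worse". The enhanced group has the same distance criterion, with DCIVA of 0.3 logMAR or better.
- **Visit.** The Visit Schedule has one visit and a numbered list of ten tests. Items 2 to 7 are monocular and then binocular acuities; binocular DCIVA is item 6. Item 8 is "Pupil measurements (photopic and/or mesopic", by automated and manual methods. Item 9 is "Review or remeasurement of biometry (IOL Master 700 or Atlas 9000 topography". Item 10 is iDesign. The list is introduced simply as the testing the subject will have, and nothing says that the order is required.
- **Questionnaire.** Study Objectives says that "the patients will also fill out a questionnaire". Primary Clinical Endpoints item 3 is a "Comparison of a patient satisfaction survey between the two groups". The questionnaire is not among the ten visit items and has no stated timing.
- **Use of the pupil and biometry data.** Primary endpoint 2 looks for between-group differences in biometric data, including pupil size. Number of Subjects lists six predictors: pupil size, q value, spherical aberration, anterior chamber depth, axial length and average K.

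**The concern.** The groups are formed from an acuity result obtained at the same visit as the pupil measurement and possibly the biometry. Whoever has seen binocular DCIVA knows, or can work out, the patient's group. The protocol's clinical hypothesis is that biometric properties such as pupil size explain better intermediate and near vision, so staff have an expectation that could colour a judgement-based reading.

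Two steps of endpoint 2 are open to this: the manual pupil reading, and the decision to accept existing biometry or repeat it. If repeats are made more readily in one group, the data source differs by group even though each measurement comes from a device.

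Endpoint 3 is self-reported and is meant to reflect everyday life. A patient who has just read well, or struggled, on the intermediate and near charts may answer differently from one who has not yet been tested. That needs no misconduct, and the patient need not be told a group.

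**Working it through.** **Step 1: does intermediate acuity alone reveal the group?** Both definitions require binocular BCDVA of 0.1 logMAR or better, so distance acuity does not separate the groups. They differ only on DCIVA: 0.4 or worse against 0.3 or better. The revealing test is therefore item 6.

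**Step 2: what comes after it in the list?**

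| Item | Test | Exposure if the numbered order is followed |
|---|---|---|
| 5 | Binocular BCDVA | Does not separate the groups |
| 6 | Binocular DCIVA | Reveals the group |
| 8 | Pupil, automated and manual | Manual reading exposed; automated reading less so |
| 9 | Biometry, reviewed or remeasured | Choice of source exposed; device values less so |
| 10 | iDesign | Device output, less exposed |
| None | Questionnaire | Exposed if given after items 3 to 7 |

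The documents do not say when to review and when to remeasure, or which pupil value (photopic or mesopic, automated or manual) is analysed.

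**Step 3: how much of endpoint 2 is affected?** One of the six predictors, pupil size, has a manual method, and an automated one is planned beside it. The other five are to come from the IOL Master, Atlas or iDesign. The exposed part is the manual pupil value and the choice of biometry source.

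**Step 4: illustration of size.** The plan gives no figure for this bias, so there is none to reproduce. The following inputs are assumptions, apart from the total of 110 patients, which is taken as stated in Number of Subjects, and the 5% alpha, which is given there without stating sidedness:

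- no true group difference;
- a spurious shift *d* of 0.1 or 0.2 SD that arises only from knowing the acuity result;
- a two-sided 5% test;
- groups of 55 and 55. No split is planned, because acuity thresholds form the groups.

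Under the normal approximation, z = d / √(1/n₁ + 1/n₂), and the rejection probability is 1 − Φ(1.96 − z) + Φ(−1.96 − z).

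- 55/55: √(2/55) = 0.191. For d = 0.1, z = 0.52 and the rate is 8.2%. For d = 0.2, z = 1.05 and the rate is 18.2%.
- 80/30: √(1/80 + 1/30) = 0.214. For d = 0.1, z = 0.47 and the rate is 7.5%. For d = 0.2, z = 0.93 and the rate is 15.4%.
- With d = 0 the rate is 5% in both cases.

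This is a simple two-group comparison, whereas endpoint 2 calls for multiple regression. It shows that a small artefact would matter at this sample size. It does not show that one will occur.

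**The case against.** The strongest reply is that a checklist is being read as a sequence. The documents do not require the numbered order, do not say who performs which test, and leave the questionnaire free to come first. That stands, and the point is therefore conditional: the order is unspecified and, as listed, acuity comes first. An unspecified order still gives no protection.

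A reader might infer that endpoint 2 rests on a hand-measured leading predictor and that the damage could not be undone in analysis. The documents support neither. No section ranks pupil size above the other predictors. An automated reading is also planned, so the analysis could use it alone or compare it with the manual one by group. Reviewed and remeasured biometry could be flagged and analysed separately, if the source is recorded.

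A reader might also infer that the test session by itself would create a link between group and satisfaction. Patients are seen 1 to 6 months after surgery, already know how they function day to day, and are nowhere said to be told their group. A real association is what endpoint 3 sets out to find. The session could add to it, by an unknown amount.

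It can also be said that acuity must come early because inclusion 4 and exclusion 10 depend on it. Both concern distance acuity, which does not separate the groups and can be checked before the other tests. Finally, staff may already know some post-operative vision results from routine care. That is fair, and it means reordering protects only in part.

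**Conclusion.** The point holds in a limited form. The visit is open-label, the group-revealing test is listed ahead of the manual pupil reading and an unruled choice of biometry source, and the questionnaire for a primary endpoint has no position. Followed as numbered, this leaves an avoidable route for bias into part of endpoint 2, and into endpoint 3 if the survey follows acuity testing.

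The size cannot be derived from the documents. The range of about 8% to 18% depends wholly on the assumed shift and the 55/55 split, and should not be read as an estimate for this trial. This is a low-cost improvement to the design. It gives no reason to think that the study's results would be invalid.

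**What to change.** State the order of the single visit in the Visit Schedule:

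1. Questionnaire.
2. Distance acuity, with the refraction it needs, if required to confirm eligibility.
3. Pupil measurement, biometry and iDesign. Decide for each patient whether biometry is reviewed or remeasured before any intermediate or near acuity is tested.
4. Intermediate and near acuity, monocular and binocular, last.

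This needs no extra staff, test, visit or patients, and the sample size is unaffected. The cost is a small change to clinic flow, and a patient found ineligible at step 2 will already have completed the questionnaire. Protection is partial, because staff or patients may already know some post-operative vision results.
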